7.2 Exploratory Endpoints

The exploratory endpoints include the following:

- Percentage of participants achieving PASI-50, PASI-75, PASI-90, and PASI-100 at Weeks 4, 8, and 12
- Percentage of participants achieving PGA of 0 or 1 with a ≥ 2 -point improvement at Weeks 4, 8, and 12
- Percentage of participants achieving PGA of 0 at Weeks 4, 8, and 12
- Mean change from baseline in PSI quality of life total and itch scores at Weeks 12 and 16

- Mean percentage change from baseline in PSI quality of life total and itch scores at Weeks 12 and 16
- Mean change from baseline in Pain and Fatigue scores at Weeks 4, 8, 12, and 16
- Mean percentage change from baseline in Pain and Fatigue scores at Weeks 4, 8, 12, and 16
- Mean change from baseline in fasting blood glucose and fasting lipid panel at Weeks 8 and 16
- Mean duration of remission in participants who achieve PASI-100
- Mean duration of treatment success in participants who achieve PASI-50
- Mean duration of therapeutic response in participants after cessation of study treatment

Biomarker endpoints (statistical analysis to appear separately from the CSR) include the following:

- Histological assessment of skin plaque biopsies (including epidermal thickness, basal mitotic counts and immune cell infiltrates) at Week 16 versus baseline
- mRNA transcription analysis on skin plaque biopsies at Week 16 versus baseline
- Blood cytokine and chemokine levels at Week 16 versus baseline
- Microbiome composition (in feces) at Week 16 and Week 20 versus baseline

Exploratory endpoints will be summarized using the mITT set, with data collected after discontinuation of treatment excluded but without consideration of any protocol deviations.

7.3 Sample Size Determination

The sample size of 225 participants in total, has been chosen to explore the tolerability and safety of EDP1815. Although the study will use a model-based probability inference approach in a Bayesian framework, the following power calculation was also performed

(using a basic frequentist approach) in order to give confidence that enough participants are available to find a clinically meaningful difference between active dose and placebo if the below assumptions are met.

The primary efficacy endpoint is the percent change from baseline in the PASI score at Week 16. Percent change from baseline relative to placebo will be estimated within the model (Section 7.6.1) as (percent change in active) - (percent change in placebo), with a negative value indicating a greater improvement for active than placebo. A percent change from baseline relative to placebo of at least 20% will be considered clinically meaningful. The pooled standard deviation across all doses is assumed to be 25%.

Participants in the placebo arm of each cohort will be pooled for the statistical analysis in order to compare active and control arms resulting in 75 participants randomized to the pooled placebo group and 50 participants randomized to each active treatment group (EDP1815 0.8×10^{11} cells, EDP1815 3.2×10^{11} cells, and EDP1815 8.0×10^{11} cells). Assuming that no more than 15% of participants will discontinue treatment before the Week 16 visit, at least 42 active and 21 placebo participants in each of the 3 cohorts are expected to provide data through the Week 16 visit.

Each pairwise comparison between pooled placebo and active dose would be expected to have more than 95% power to detect a difference between the treatment groups at the 5% significance level under the assumption that pooling the placebo groups is a valid strategy. If the 3 placebo cohorts are considered to be too heterogeneous for pooling into a single reference group, the power to detect a difference in each within-cohort pairwise comparison between active and placebo doses would be greater than 80%.

As the statistical inference for this study will focus on estimation rather than testing a formal hypothesis, no multiplicity adjustments of the different comparisons between groups in order to control the study-wise type I error rate will be performed.

Similarly, as there is no intention to use any interim analyses to stop the study early for efficacy (Section 7.6.7), no adjustments for multiplicity will be made to account for any analyses performed as part of the interim analyses.

7.4 Analysis Sets

The following analysis sets will be used in the statistical analyses.

Enrolled set: The enrolled set will consist of all participants who sign the ICF.

mITT set: The mITT set will consist of all participants who were randomized to treatment and who received at least one dose of study treatment. Participants who withdraw from the study before the end of Week 4 and are replaced will be included in this analysis set. All analyses using the mITT will group participants according to randomized treatment.

PPS: The PPS will consist of all mITT participants who were not replaced (following study withdrawal before the end of Week 4) and who do not have a protocol deviation that may impact efficacy with a start date for the deviation before initiation of study treatment. Note that in the case of participants who have a protocol deviation with a potential impact on efficacy after initiation of treatment, the participant will remain in the PPS but all data collected after the protocol deviation occurred will be excluded from any analyses performed using the PPS. All analyses using the PPS will group participants according to treatment received at the start of the study. Deviations that may affect efficacy are shown in Table 7-2.

Week 16 responders set: The Week 16 responders set will consist of all mITT participants who achieved a PASI-50 response at Week 16.

Safety set: The safety set will consist of all participants who received any study drug. All analyses using the safety set will group participants according to treatment received. If participants received multiple treatments during the study, they will be assigned to treatment group in the following manner:

- If participant received both active EDP and placebo treatments, they will be assigned to the active treatment group.
- If participant received 2 or more different active dose levels, they will be assigned to the treatment they received for the longest period.

The mITT set will be the primary population of interest for the efficacy section, with some supportive analyses performed using the PPS. The safety set will be used for all safety summaries.

Table 7-2 Deviations with a Potential Impact on Efficacy

Description	Evaluation Period	Impact on PPS analyses
Not meeting inclusion criteria 3, 4, or 6 or meeting any of exclusion criteria 1-12 or 27	Baseline	Exclude participant from PPS.
Use of any prohibited medication (Section 5.8.2.1)	Throughout study	If start date of prohibited medication \leq date of first dose of study drug then exclude participant from PPS. Otherwise, include participant in PPS but exclude all data collected on or after start date of prohibited medication.
Compliance with study drug <80%	Evaluated in 8-week periods (Weeks 1-8 and 9-16)	If participant is non-compliant within Week 1-8 treatment period, then exclude from PPS. If participant is non-compliant only within Week 9-16 treatment period, include participant in PPS but exclude all data collected after the Week 8 visit date.
More than 7 consecutive days with no study medication without participant being permanently withdrawn from study medication	Throughout study	Participant will not be excluded from PPS, but all data collected after the 8th consecutive day with no study medication will be excluded.
More than 14 total days with no study medication (does not need to be continuous)	Throughout study	Exclude participant from PPS.
Incorrect study treatment taken	Throughout study	Participants will not be excluded from PPS. If a participant received a study drug other than that received at the start of the study, then exclude all data collected on or after the date at which the treatment change occurred.
Study treatment blind broken	Throughout study	If participant's blind is broken prior to first dose of study drug then exclude from PPS. Otherwise, include participant in PPS but exclude all data collected on or after the date on which the blind was broken.

7.5 Description of Subgroups to Be Analyzed

Results may be summarized by individual cohort.

Subgroup analysis of the primary estimand will be performed based on the following subgroups:

- Baseline PASI score (<10, ≥ 10)
- Baseline PGA score (2, 3)
- Baseline BMI ($<30 \text{ kg/m}^2$, $\geq 30 \text{ kg/m}^2$)

If the placebo groups from the 3 cohorts are found to be too heterogeneous to be pooled (Section 7.6.1), the primary and secondary analyses will be performed using within-cohort comparisons of active and placebo treatments, and summary tables may also be produced by cohort.

7.6 Statistical Analysis Methodology

Statistical analysis will be performed using SAS software Version 9.3 or later.

In addition to the inferential analyses described in Sections 7.6.1 and 7.6.2, descriptive statistics will be provided to summarize all endpoints by treatment group.

Continuous variables will be summarized using the mean, standard deviation, median, minimum value, and maximum value. Categorical variables will be summarized using frequency counts and percentages. Time-to-event variables will be summarized using Kaplan-Meier estimates of the proportion of participants with the event at each visit. Data will be listed in data listings.

Details of the statistical analyses, methods, and data conventions will be described in the SAP.

7.6.1 Analysis of Primary Efficacy Endpoint

The assumption that the 3 cohorts of placebo participants can be pooled into a single placebo group to be used as a control for all active doses will be examined using mean ($\pm \text{SD}$) plots and box plots of percent change in PASI score against time. In addition, an MMRM will be used to compare the 3 cohorts of placebo participants. The model will include parameters for cohort, visit and baseline PASI score together with cohort*visit and baseline PASI score*visit interactions. Least squares mean (95% CI) estimates for each placebo cohort will be plotted by visit.

A decision will be made by the Evelo study team, based on examination of the above figures and model, on whether the pooling strategy is appropriate.

The primary analysis will be performed using a Bayesian MMRM. The model will include parameters for treatment*visit and baseline PASI score*visit interactions. Body mass index, gender, country, and time since diagnosis will also be considered and included as parameters if found to be significant ($p < 0.05$). The model will not include an intercept. Visit will consist of 6 levels (Weeks 1, 2, 4, 8, 12, and 16) and treatment will consist of 4 levels (pooled placebo, EDP1815 0.8×10^{11} cells, EDP1815 3.2×10^{11} cells, and EDP1815 8.0×10^{11} cells) if the placebo pooling strategy is considered appropriate or 6 levels (Placebo matching EDP1815 0.8×10^{11} cells, Placebo matching EDP1815 3.2×10^{11} cells, Placebo matching EDP1815 8.0×10^{11} cells, EDP1815 0.8×10^{11} cells, EDP1815 3.2×10^{11} cells, and EDP1815 8.0×10^{11} cells) if the placebo pooling strategy is not considered appropriate.

The priors for all parameters in the model will be non-informative and follow a normal distribution with mean 0 and SD 1000. The prior for the variance-covariance matrix will follow an inverted Wishart distribution with degrees of freedom equal to the number of visits and an identity scale matrix. The choice of Wishart distribution is based on it being the conjugate prior of the inverse-covariance matrix of a multivariate-normal random vector.

If the assumption of similarity between the 3 placebo cohorts is considered appropriate, the placebo cohorts will be pooled, and a single placebo control group will be used for the pairwise differences for each active dose to placebo. If the assumption of similarity is considered inappropriate, each placebo dose will be included in the model as a separate dose level and pairwise comparisons between each active dose and placebo will be performed using only the matching placebo dose data for the relevant active dose.

The adjusted posterior mean percentage change from baseline and the associated 95% HDP CrI for each treatment at Week 16 will be reported, together with the adjusted mean difference from placebo and the associated 95% HDP CrI for each active dose at each visit and the probability that each treatment difference is less than 0%, -20%, -30%, and -50%.

Model checking and diagnostic plots, including posterior density plots of the posterior samples for all parameters in the model and residual plots to evaluate the distributional assumptions underlying the model, will be produced. The assumption that data are missing at random will be evaluated by plotting the mean percentage change in PASI score against visit,

by treatment group, for the subgroups of participants who completed 16 weeks of study drug compared with those who discontinued study drug before the Week 16 visit.

If model checking and diagnostic plots show a violation of the assumptions underlying the analysis, alternative statistical methods will be considered, appropriate to the type of violation observed.

This primary analysis will be repeated using the 3 supportive estimands defined in Section 7.1.1.

If the assumption of similarity between the placebo cohorts is supported, a supplementary analysis will be performed on the percent change from baseline to Week 16 in PASI score using a dose-response model on the pooled cohorts. The log-linear, 3-parameter, and 4-parameter E_{max} models will be fitted and compared, with the best fitting model (lowest DIC) selected for use in the outputs.

The dose-response model will be fitted to the data using Bayesian techniques with noninformative priors for E_0 and E_{max} and an FUP for ED50 (3- and 4-parameter models only) and the slope parameter m (4-parameter model only). The rationale for this choice of inference is that the FUP shrinks the dose response towards a flat line throughout the dose range, therefore providing more conservative estimates of the dose-response relationship compared to maximum likelihood (Bornkamp 2014). The models will be fully described in the SAP.

Based on the selected model, the posterior mean with associated 95% HDP CrI, for the difference from placebo for each active dose will be produced for the pairwise differences between each active dose and placebo, together with the posterior mean and 95% HDP CrI of the treatment difference from placebo for each active dose and posterior probabilities that difference from placebo is less than 0, -20%, -30%, and -50%. A further sensitivity analysis will be performed on the dose response model, in which participants who withdrew from study drug due to treatment will have their Week 16 percentage change from PASI imputed as 100% after study drug was discontinued.

Percent change from baseline in PASI score will be summarized by visit.

All summaries and analyses defined above for the primary estimand will be repeated using the subgroups defined in Section 7.5.

7.6.2 Analysis of Secondary Efficacy Endpoints

All secondary analyses will be performed either using the pooled placebo group if the assumption of similarity for the placebo cohorts is considered appropriate or using the 3 cohort-level placebo groups if it is not considered appropriate.

Unless otherwise specified, all secondary analyses will be performed on the mITT set, excluding data collected after treatment discontinuation, without consideration of any protocol deviations. Dose will be treated as a categorical variable and no dose response modelling will be done. Comparisons of interest will be between individual EDP1815 doses and placebo. All p-values, posterior probabilities, CI, and CrI calculated will be considered as descriptive with no further adjustments for multiplicity performed.

Data will be analyzed as collected and no imputation of missing data will be performed.

The covariates selected for the Bayesian MMRM analysis for the primary estimand will also be used in all other analytical models including covariates.

Mean percentage change from baseline in PASI score at Weeks 4, 8, and 12 will be analyzed as part of the MMRM for the primary estimand. The same statistics produced for the Week 16 time point will also be produced at Weeks 4, 8, and 12.

The following secondary endpoints will be analyzed in the same manner as described for the primary analysis:

- Mean absolute change from baseline in PASI score at Weeks 4, 8, 12, and 16
- Mean percentage change from baseline in LSS at Weeks 4, 8, 12, and 16
- Mean absolute change from baseline in LSS at Weeks 4, 8, 12, and 16
- Mean percentage change from baseline in PGA×BSA at Weeks 4, 8, 12, and 16
- Mean absolute change from baseline in PGA×BSA at Weeks 4, 8, 12, and 16

- Mean percentage change from baseline in DLQI score at Weeks 4, 8, 12, and 16
- Mean absolute change from baseline in DLQI score at Weeks 4, 8, 12, and 16
- Mean percentage change from baseline in mNAPSI total score at Weeks 4, 8, 12, and 16
- Mean absolute change from baseline in mNAPSI total score at Weeks 4, 8, 12, and 16

For the PASI-50, a generalized linear mixed effects model with a logit link function will be fitted using data from all visits. Treatment, visit, and baseline PASI score terms will be included in the model as fixed effects, together with treatment*visit and baseline PASI score*visit interactions, and any baseline covariates selected in the primary analysis model for the primary estimand. Odds ratios and 95% CIs for each active dose compared to placebo at each visit will be presented.

A supportive analysis for the PASI-50 will also be performed, in the same manner as described above, in which participants who withdraw from study drug before Week 16 due to requirement for alternative therapy will be included in the model with the PASI-50 endpoint imputed as ‘not achieved’ at all expected visits after study drug withdrawal.

A sensitivity analysis will also be performed on the PASI-50. Bayesian logistic regression models will be individually fitted at each of Weeks 4, 8, 12, and 16. The model will include parameters for treatment and baseline PASI score together with any baseline covariates selected in the primary analysis model for the primary estimand. The posterior odds-ratios for each pairwise comparison of an active EDP1815 dose and placebo with associated 95% HDP CrI will be presented together with the posterior probability that the true odds ratio >1.

Percentage of participants achieving PGA of 0 or 1 with a ≥ 2 -point improvement and percentage of participants achieving a PGA of 0 will be analyzed in the same manner as described above for PASI-50 with the exception that the sensitivity analysis using the Bayesian logistic regression model will only be fitted on the Week 16 data.

For the time to first achievement of PASI-50, a nonparametric survival analysis for interval censored data will be performed. The expectation-maximization iterative complex minorant (EMICM) method for iterative computation of the nonparametric maximum likelihood

estimator for the survival function (Wellner and Zahn 1997) will be used. The number and proportion of participants who meet the PASI-50 at least once during the study will be presented. A generalized log-rank test will be used to compare each active dose with placebo and the p-value for treatment difference will also be presented. The estimated survival curves for each treatment group will also be presented.

Cumulative incidence of partial relapse and complete relapse at Weeks 20, 24, 28, and 40 will be summarized by treatment group on the Week 12 responders set.

Cumulative incidence of rebound after cessation of study treatment at Weeks 20, 24, 28, and 40 will be summarized by treatment group.

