7.7 Visit Windows

All data will be reported according to nominal visits, except for subjects who complete the follow-up Week 20 assessments due to withdrawing from the study before the Week 16 visit. For example, if a Week 2 visit occurred on Day 16 instead of the nominally expected Day 14 it will be reported and included in the summary statistics/statistical analyses for Week 2.

Subjects who withdraw prematurely from the study should complete the assessments required for the follow-up visit (Week 20). However, this data will only be included in tables and figures which are produced **by visit** for subjects who completed the 16-week treatment period and provided Week 16 data prior to the Week 20/follow-up data being collected. Tables and figures which do not show summaries by visit and all listings will include all collected Week 20/follow-up data regardless of whether the subject completed the 16-week treatment period.

Scheduled visits which occur outside the protocol-specified visit window (e.g. if the Week 2 visit occurred on Day 19 outside of the Day 12-18 window), this will be noted as a protocol deviation but data collected will still be included in all summary and analysis tables.

Unscheduled visits will not be included in summary or analysis tables, unless they are baseline measurements or provide data towards a safety endpoint which looks at worst-case post-baseline.

8 Summary of Study Data

All continuous variables will be summarized using the following descriptive statistics: n (non-missing sample size), mean, SD, median, maximum and minimum. The frequency and percentages (based on the non-missing sample size) of observed levels will be reported for all categorical measures.

In general, all data will be listed, sorted by randomized treatment (Placebo, EDP1815), cohort (1, 2, 3), site number and participant number. Relevant listings will include whether the assessment was performed and the date, study day/visit and time of the assessment as applicable.

Unless otherwise specified below, all summary tables will be structured with a column for each treatment. Where appropriate, columns combining all placebo participants, all EDP1815 participants and an overall total column may also be presented.

For summaries of study disposition, demographic and baseline data and study treatment compliance, columns will be ordered and labelled as follows:

- Placebo 1 capsule
- EDP1815 1 capsule
- Placebo 4 capsules
- EDP1815 4 capsules

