The number and percentage of responders will be reported at each visit together with 95% CI for the percentage of responders, calculated using the exact method for binomial proportions. At each visit, the adjusted odds ratio, with 95% confidence interval (CI) associated p-value will also be presented. If the analysis is changed to exclude visits, then only the summary statistics for the number of subjects with data, the number and percentage of participants with a response and the 95% CI for the percentage of responders will be shown for any visits which were excluded from the model. Table footnotes will be added as appropriate to detail any changes to the planned analysis.

The adjusted odds ratios (with 95% CI) will be plotted by visit for the 3 active doses compared to placebo.

In addition, for the PASI-50 response endpoint only, a supportive analysis will be performed using the following supportive estimand. The estimand will differ only in the intercurrent event strategy.

Table 5 Intercurrent Event Strategy for Secondary Supportive Estimand for PASI-50

Estimand	Purpose	Population	Intercurrent Event Strategy
Secondary Supportive Estimand 1	Assess the impact of treatment discontinuation due to requirement for alternative therapy	miITT	Protocol deviation with potential to impact efficacy Treatment policy (as per Secondary estimand) Treatment discontinuation due to requirement for alternative therapy before Week 16 Composite (PASI-50 will be considered as not achieved at all scheduled visits after treatment discontinuation) Treatment discontinuation for any other reason before Week 16 While on treatment (as per Primary estimand)

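### The SAP limits the failure-imputed supportive analysis to PASI-50 although the protocol's wording carries it to both PGA endpoints, and the descriptive responder percentages leave out participants who discontinued

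*Protocol*

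**What the plan says.** **Protocol 7.6.2.** Secondary analyses use the mITT set and exclude data collected after treatment discontinuation; "Data will be analyzed as collected and no imputation of missing data will be performed". For PASI-50 three analyses are described: a generalized linear mixed model (GLMM) on all visits; a supportive version in which participants who stop study drug before Week 16 because they need alternative therapy are scored as not achieving PASI-50 at later expected visits; and Bayesian logistic regressions at single visits. The two PGA endpoints (PGA 0 or 1 with at least a 2-point improvement, and PGA 0) "will be analyzed in the same manner as described above for PASI-50 with the exception that the sensitivity analysis using the Bayesian" logistic model is fitted at Week 16 only.

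**SAP 9.5 and 9.5.3.2.** Section 9.5 rules out further supportive or sensitivity analyses for the secondary endpoints apart from PASI-50 and DLQI. Section 9.5.3.2 says that "for the PASI-50 response endpoint only, a supportive analysis will be performed using the following supportive estimand". The output list has a Secondary Supportive Estimand 1 table for PASI-50 (14.2.3.1.2) but none among the PGA tables (14.2.8.1, 14.2.8.2, 14.2.9.1, 14.2.9.2). SAP Table 8, the list of changes from the protocol, does not mention this.

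**SAP denominators.** Section 5.3.3.1 and Table 3 set scores to missing after treatment discontinuation, with a 4-day allowance in Table 3 that Section 9.5 carries to the secondary endpoints. Section 8 (Summary of Study Data) fixes the denominator: "The frequency and percentages (based on the non-missing sample size") are what is reported for categorical measures. Section 9.5.4 gives PASI-75/90/100 as counts and percentages with exact confidence intervals, and no model.

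**The concern.** There are two separate matters.

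The first is a protocol–SAP mismatch. The protocol names a single exception when it carries the PASI-50 methods over to PGA, and that exception does not concern the supportive analysis. The SAP removes the analysis for PGA without declaring a change.

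The second concerns what the responder percentages describe. Protocol 4.2 and SAP 5.1 define treatment failure as starting another psoriasis therapy of the listed kinds. A participant who stops for that reason before Week 16, with no assessment inside the 4-day allowance, is a known failure but leaves the Week 16 denominator. SAP 7.3 relies on mixed models to deal with missing data, and PASI-75/90/100 have none. The Bayesian logistic regressions in SAP 9.5.3.3 use one visit at a time, as would the Week 16 logistic regression that SAP 9.5.3.2 permits in place of the GLMM when responders are few. If discontinuation differs between arms, the comparison of percentages shifts as well as their level.

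**Working it through.** **Inputs from Protocol 7.3.** Group sizes: "75 participants randomized to the pooled placebo group and 50 participants randomized to each active treatment group", hence 25 placebo per cohort. Discontinuation before Week 16: at most 15%. Effect: "A percent change from baseline relative to placebo of at least 20% will be considered clinically meaningful". Spread: "The pooled standard deviation across all doses is assumed to be 25" percent. Claim: "more than 95% power to detect a difference between the treatment groups at the 5% significance level" for pooled placebo, and above 80% within cohort. Two-sided testing is assumed, since sidedness is not stated. No responder rate or responder power is given anywhere.

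**The plan's own figures.** Retained: 50 × 0.85 = 42.5 (42 stated) and 25 × 0.85 = 21.25 (21 stated), so pooled placebo is 3 × 21 = 63. Power, normal approximation, Φ(20/SE − 1.96):
- 63 v 42: SE = 25 × √(1/63 + 1/42) = 4.98; power 98.0% (noncentral t 97.8%).
- 21 v 42: SE = 25 × √(1/21 + 1/42) = 6.68; power 84.9% (noncentral t 83.8%).

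Both stated bounds hold. They concern the primary endpoint, and nothing here alters the sample size.

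**Effect on a percentage.** With x responders, the observed-case rate is x/42 and the full-mITT rate x/50, a ratio of 50/42 = 1.19. For placebo it is 75/63 = 1.19. (Unrounded, 1/0.85 = 1.18.) Example with assumed counts: 13/42 = 31.0% v 9/63 = 14.3%, difference 16.7 points, becomes 13/50 = 26.0% v 9/75 = 12.0%, difference 14.0 points.

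**Effect on an odds ratio.** Assume observed rates of 30% active and 15% placebo: OR = (0.30/0.70)/(0.15/0.85) = 2.43. Counting every discontinuation as non-response multiplies each rate by (1 − d), where d is the arm's discontinuation proportion:

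| d active | d placebo | Active | Placebo | OR |
|---|---|---|---|---|
| 15% | 15% | 25.5% | 12.75% | 2.34 |
| 15% | 5% | 25.5% | 14.25% | 2.06 |
| 25% | 10% | 22.5% | 13.5% | 1.86 |
| 5% | 15% | 28.5% | 12.75% | 2.73 |
| 10% | 25% | 27.0% | 11.25% | 2.92 |

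The last row mirrors the third. Over 150 active and 75 placebo participants, 25%/10% is (37.5 + 7.5)/225 = 20% overall, above the plan's 15%; 10%/25% is (15 + 18.75)/225 = 15%.

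**What the sums do not measure.** They treat every discontinuation as failure. Secondary Supportive Estimand 1 does so only for stops due to alternative therapy, and the documents do not say how many those will be. The consequence of the PGA omission alone therefore cannot be computed.

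**The case against.** On-treatment handling without imputation is a declared estimand in both documents (Protocol Table 7-1; SAP 9.4.1 and 9.5). Counting every leaver as a non-responder answers a different question. A reader might infer that the planned responder rates are simply wrong or overstated. The documents do not support that: the rates estimate what the plan says they estimate, and the added row is a supplement. This part of the objection stands.

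A reader might also infer that the PGA endpoints have no protection against dropout. That is not so. Their main analysis is the all-visit GLMM (SAP 9.5.3.2), which keeps earlier on-treatment visits under missing at random. What PGA lacks is a failure-imputed analysis. The exploratory apremilast comparisons (SAP 9.6.2.1) also carry the last value forward for PASI-75 and PGA response, so leavers stay in those denominators, although carrying forward is not failure imputation and one comparison depends on outside results being published in time.

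A third tempting reading is that dropping leavers always flatters the drug. The table shows movement in both directions; if failure drives stopping, heavier placebo dropout is at least as plausible.

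It is also fair to say that the protocol never names the supportive analysis for PGA, so its extension rests on the plain reading of one sentence. Tables give responder counts, and SAP 8.1 tabulates discontinuations with reasons, so a reader could rebuild the full-mITT percentages. No formal hypothesis is tested and secondary results are descriptive. These points limit the consequence. They do not explain why the SAP departs from the protocol without saying so.

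**Conclusion.** The point holds in two limited parts, and it is a minor one. The PGA restriction is an undeclared inconsistency between protocol and SAP, on the ordinary reading of the protocol sentence. The denominator issue is a design weakness confined to the descriptive percentages, most clearly PASI-75/90/100, and to the single-visit logistic models.

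The factor of about 1.19 rests on the plan's 15% discontinuation in every arm and on counting all discontinuations as non-response; participants assessed within the 4-day allowance would reduce it. The odds-ratio figures rest on assumed responder rates and dropout patterns. They show a small shift when dropout is balanced and a larger one, of either sign, when it is not.

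**What to change.** 1. In SAP 9.5, 9.5.3.2 and the output list, apply Secondary Supportive Estimand 1 to both PGA endpoints, in line with the protocol. If its removal is intended, list it in Table 8 with a reason.
2. In the PASI-50/75/90/100 and PGA tables, add a supportive row giving responders over all mITT participants in the arm, with discontinuation counted as non-response.
3. Leave the main analysis unchanged.

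The cost is a few extra outputs and the additional PGA GLMM runs, which may meet the sparse-response difficulties that SAP 9.5.3.2 already anticipates. The supportive rates will look less favourable, partly for reasons unrelated to efficacy: the mITT set keeps participants replaced before the end of Week 4 alongside their replacements, and an all-mITT denominator also absorbs visits missed for other reasons such as COVID-19. A footnote with those counts, drawn from the SAP 8.1 summaries, would let readers judge the row.
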